Problem Solving is strongly promoted by VA Mental Health Service Line. That group has conducted pilot studies looking at rolling out PST in that context; but they have communicated to us an interest in evaluating problem solving in physical health as well. [name] ongoing work with with VA problem solving leaders (ie, [name], VA Senior Consultant/Liaison for Psychological Health, (59)) will allow us to inform them on the potential use of problem solving in prevention, and will also allow us to implement this aspect of our intervention with relative ease.

Group Visits have been mandated by VA as part of PACT (60). They are thought to represent an efficient means to provide access to high-quality care, and there is evidence that they meet that goal for patients with serious chronic illness, including in the VA (11, 61-63). However, group visits for patients without severe or symptomatic chronic illness have not been studied well. This proposal allows PACT to determine the role of group visits for relatively healthier patients; it may define the limits of the group model in VA, or allow VA to confidently expand group care to a much wider range of patients.

D. RESEARCH DESIGN AND METHODS

D.1 Study Design. We propose a randomized, controlled trial (RCT) of our GPC intervention (details in section D.5 below). Outcomes will be measured at baseline, 6, and 12 months after enrollment. The control group will receive usual care.

D.2. Setting. We will perform the study among patients at the Durham and Buffalo VAMCs. Multiple VAMC settings are used to increase generalizability, and to increase numbers of eligible patients. [name], key personnel on this grant, is core faculty of a VA Mental Health Center of Excellence, the VISN 2 Center for Integrated Healthcare (CIH). The goal of CIH is to integrate behavioral health into primary care. The center has numerous research projects ongoing at all times; research personnel at CIH are on staff at Buffalo VAMC. Buffalo will be treated as an equal site for the scientific protocol, with the goal of approximately equal enrollment from Buffalo and Durham.

D.3. Patients. The patients will be 400 VA users (see enrollment feasibility, D.3.c.v, and sample size, D.9, below) without prior history of cardiovascular event, but with at least 5% risk of such an event, with at least 2% of that risk potentially reversible.

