D.4.a. Randomization. The project's masters-level statistician will maintain a computer generated, patient randomization sequence separate from the site of patient enrollment. The group assignment will be communicated to the opposite site RA (ie, Durham patients will receive a randomization call from the Upstate NY RA, and vice-versa). That RA will make the phone call at the appointed time, and explain the implications of the arm assignment to the subject. This will allow the local RA to remain blinded to arm assignment for follow-up evaluation. Randomization will be stratified by site and gender. Patients randomized to the GPC arm will be offered a choice of one of a few possible half-days for their group session to meet, and that choice will lead to the patient's assignment to a particular GPC group.

D.5. Intervention. The GPC intervention will be delivered to patients in the active arm. The basic structure is that of a group problem-solving intervention, with interval phone calls delivered to check in on goal progress and reinforce group learning. Groups will meet monthly for 6 months, and each patient will be called once between each group session. Based on our experience with delivering problem solving groups (JN), each group will consist of 10 patients. In general, problem-solving principles will represent the content of the group sessions. Problem solving theory is described in greater detail above (B.4). Again, problem solving intends to teach patients to overcome internal barriers to healthful behaviors. We will directly assess the effects of problem solving in our intervention by use of the CD-RISC (D.8.b.iii.b).

The problem solving orientation will be combined, at all group sessions, with the typical self-efficacy training used in SMGs, so that patients will be taught simultaneously to overcome both internal and external barriers. Similar to our prior studies (eg, CouPLES (56)), participants will be asked to develop personal goals related to CVD-related behaviors (e.g., smoking and weight reduction). We will directly assess the coaching effects by measuring self-efficacy across chosen behaviors using the Patient Activation Measure (PAM, D.8.b.ii.a below)

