D.5.b. Intervention personnel. The groups will be coordinated by a person with a Masters in Social Work (MSW) hired for the research enterprise but trained and credentialed identically to a facility's Health Behavior Coordinator (HBC). Each facility now has an HBC, and the work of the HBCs is coordinated by the NCP. The role of a facility's HBC is to be the lead interventionist in implementation efforts toward preventive health, and to use behavioral techniques to achieve these goals. HBCs are almost all either clinical psychologists or MSW-level social workers, and all are trained in behavior change techniques (e.g., motivational interviewing; see section D.7 for details). Additionally, NCP plans to train HBCs in problem-solving in the near future. It is this training in multiple approaches to behavior change that makes the HBC the appropriate interventionist for GPCs. We will use either an HBC or HBC equivalent so that if GPCs are effective, they can be easily implemented with the personnel already assigned at each VAMC.

The phone calls associated with the intervention will be performed by a healthcare coach, who will work closely with the group interventionist. Coaches are relatively inexpensive personnel who are in wide use across the private sector for telephone counseling. The rationale for the use of coaches is also based on translation of the intervention; at some facilities, HBCs are looking to hire and train sub-RN-level personnel to deliver behavior change interventions that the HBC would coordinate. There is no need for a masters- or RN-level trained person; coaching interventions are normally (and successfully) delivered by coaches without that level of training (3, 26, 27). However, the intervention coaches will be trained in coaching techniques in general, and in MI in particular, prior to starting the intervention (28).

D.5.c. Intervention structure. As soon as 10 patients at a site have been randomized to the intervention arm that are willing to attend on a given half-day, a group will be formed and patients will be called and notified

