about the time and place. Our experience is that the half-day will be set and the first visit will occur within 2-4 weeks of the enrollment visit for each patient. Groups will meet every month for 6 months. The same 10 patients will meet each time with the same group facilitators, on the half-day of the week chosen as described above. Group sessions will last 90 minutes; the first 20 minutes are set aside for social interaction as a means to engage the patients (11), and the remaining 70 minutes are for content delivery (see D.5.d). Phone calls will be made once to each patient in the interval between group sessions.

D.5.d. Attendance Enhancement Strategies. Above and beyond the usual encouragement to attend group sessions, we will attempt to increase attendance by having patients sign attendance contracts. Behavioral contracts have been shown in randomized, controlled trials to improve attendance to group sessions (66, 67). Patients will sign the attendance contract immediately upon arriving to the first group session. In addition to contracts, we will offer a cash reimbursement of \$25, similar to the expected travel pay for a clinic visit for a patient living 20 miles away, for patients attending group sessions. In our hands, session attendance has been approximately 80% using this combined approach (11).

D.5.e. Group Session Content. The group session content is taken from pre-existing group problemsolving session content, and modified to reflect both the focus on cardiovascular prevention rather than on mental health concerns as well as the self-efficacy training orientation.

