D.9.b. Missing Data. Because the main predictors of interest, intervention arm and demographics, are collected at baseline, we do not anticipate much missing data in these variables. There may be missing values in the outcome measures due to drop-out, a missed interim assessment, or item non-response. Given a thorough understanding of the missing data mechanism, it is possible to use all of the available information in analysis, rather than using only subjects with completely observed information. Our main analysis technique, general linear mixed models via maximum likelihood estimation, implicitly accommodates missingness when missingness is due either to treatment, to prior outcome, or to other baseline covariates included in the model (81), defined as missing at random (MAR). Therefore, inferences will be valid even if we have differential dropout by intervention arm. If the missing values are related to other measured patient factors, such as age, gender, or employment status, then multiple imputation (MI) provides a framework for being able to incorporate information from these auxiliary variables while still preserving a parsimonious main treatment effect model (82) and is described as a significant advantage in recommendations from Panel on Handling Missing Data in Clinical Trials (2010) (83). Depending on the type and scope of missing data MI will be conducted via the SAS procedure PROC MI or the SAS macro IVEware (http://www.isr.umich.edu/src/smp/ive/) (84). If the probability of dropout is related to the actual missing response (which is unobserved because it is missing) or to other unobserved quantities, the missing data due to dropout is considered missing not at random (MNAR) or nonignorable (85). There is a possibility that data may be MNAR, and we propose as additional sensitivity analyses to explore MNAR methods, including selection and pattern-mixture models as recommended by Molenberghs and Kenward (86).

D.9.c. Intent-to-Treat Analysis. All of the proposed primary and secondary analyses focus on the effect of GPC as compared to usual care. We, therefore, plan to use the intent-to-treat assumption for all analyses.

D.9.d. Primary Analysis. The GPC vs usual care comparison in Framingham risk score change from baseline to month 6 will be examined with the following general linear mixed model,

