The first σ^2 in the braces corresponds to the variance for the usual care control group, while the $\sigma^2[1 + (m-1)\rho]$ incorporates the design effect in GPC intervention arm (only).

The anticipated SD of the change in FRS was derived from previous studies, with a value of 6.3%. We have observed a baseline mean of 29% (SD = 14%) and a correlation between 6 month intervals of 0.9 (3). With respect to p, we have observed values in the previous studies of 0.03 (11). Finally, we took m = 10 as the average size of the prevention coaching groups.

Applying these assumptions results in a sample size of 180 per arm, or n=360 patients total. We further inflate the sample size to account for a possible 10% attrition rate by the 6-month follow up. Therefore, we plan to enroll n=400 patients total to detect a 2.0% between-arm difference in the change from baseline to month with 80% power and a type-I error of 5%.

D.10. DATA MANAGEMENT AND QUALITY CONTROL

D.10.a. Data Management Procedures. We will use a series of asynchronously connected database applications, over which a comprehensive data model will be deployed. Each database application will function independently as a discrete system. All data transactions within and between subsystems will run through secure transactions to ensure database integrity and privacy. Study data will be maintained on secure servers for the duration of the study and as long after the completion of the study as required by VA regulations at the time of study closure. All study data will be backed up on a nightly, monthly, and annual schedule.

All server hardware has built-in redundant systems. Technicians will constantly monitor server hardware, operating system and database service performance. Workstations, laptops, and any other devices will be supported in order to ensure high performance and secure operation. The primary database technology will be Microsoft SQL Server. All automated systems will run using the Microsoft SQL Server Management Agent. Automated processes will be monitored daily. The system will be configured to notify the HSR&D IT Group if an automated process fails to run successfully. The data collected during in-person interviews will be entered directly into our third party survey application named "DatStat Illume" running on an encrypted, password-protected laptop (www.datstat.com/). This survey application has been developed using Microsoft Visual

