Beyond the usual scientific presentations, our partnership with NCP presents us with a unique opportunity for rapid dissemination of our intervention, should it be effective. Our intervention was developed in direct partnership with NCP, and they had significant creative input into the intervention content. Also, our interventionists are mirror images of the HBCs hired by each VAMC with dollars provided by NCP, and NCP retains significant control over the roles of the HBCs at the facilities. Thus, if the intervention appears to improve primary prevention, NCP may use its influence over the HBCs to strongly suggest and support the implementation of the GPC intervention. Additionally, [name] has experience in implementation of prior group interventional studies—he is currently assisting VISN 7 in implementing shared medical appointments in diabetes—and he will be willing and able to do the same for this intervention. Finally, CIH, which maintains a website, frequently leads trainings supporting Primary Care-Mental Health Integration, and hosts a VA mail distribution list (Mental and Behavioral Health in PACT), will further support dissemination of successful findings in collaboration with NCP.

F. PROJECT MANAGEMENT PLAN

We will recruit a total of 400 patients from the 2 participating sites (Durham, Buffalo) over a 24-month period. This will lead to at most 1200 patient encounters over the 2 years of enrollment plus follow-up for the study, or approximately 2.5 encounters per day. We propose a 48-month study (a Gantt chart is below). We request six months to finalize the interventions, protocols, and train personnel. There will be 24 months of recruitment in which in-person interviews will take place. Based on our prior experience on group visit studies, we will enroll 4 patients per week for a total of 400 patients in 24 months. Patients will then be followed for a total of 12 months. The final 12 months of the grant will also be devoted to planning analyses, writing data analysis programs, preparing data for archiving, and preparing reports.

	1-6 month	7-12 month	13-18 month	19-24 month	25-30 month	31-36 month	37-42 month	43-48 month
Intervention programming	*							
Hiring, training	*							
Patient Recruitment		*	*	*	*			
Intervention		*	*	*	*	*		
Follow-up visits			*	*	*	*	*	
Data entry & cleaning			*	*	*	*	*	*
Analysis/Manuscripts							*	*

Protection of Human Subjects

A. Risks to Human Subjects

1. Human Subjects Involvement and Characteristics.

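### The expected 2-4 week wait for a first group session does not fit steady accrual at the planned rate, so many GPC patients could reach month 6 before session 6

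*Combined protocol and SAP*

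**What the plan says.** All references are to the combined protocol and SAP.

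- **Start of groups.** D.5.c forms a group "As soon as 10 patients at a site have been randomized to the intervention arm that are willing to attend on a given half-day". The same ten then meet throughout, monthly for six months. D.5.c adds, as the team's experience, that "the first visit will occur within 2-4 weeks of the enrollment visit for each patient". D.4.a says GPC patients are "offered a choice of one of a few possible half-days for their group session to meet"; the number is not given.
- **Accrual.** Section F says "we will enroll 4 patients per week for a total of 400 patients in 24 months". D.2 has two sites "with the goal of approximately equal enrollment from Buffalo and Durham". D.9.e (sample size) implies equal arms: "Applying these assumptions results in a sample size of 180 per arm".
- **Visits.** D.1 says "Outcomes will be measured at baseline, 6, and 12 months after enrollment". The primary analysis (D.9.d) is of "Framingham risk score change from baseline to month 6". No section ties visits to session 1 or sets a visit window.
- **Aim 3.** D.9.f lists three cohesion predictors of FRS change to month 6: the individual's last-session score, the individual's change from first to last session, and the group's last-session mean.

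**The concern.** The 2-4 week figure is the plan's only statement of when the intervention starts, and it is what places session 6 before the primary visit. If groups fill more slowly, part of the GPC arm is measured for the primary outcome before the six-session program ends. Three things follow:

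- Month 6 is not the end of intervention for those patients, which could dilute the primary effect.
- Month 12, which D.4 uses to see whether effects fade once contact stops, follows a contact-free interval that varies between patients.
- In Aim 3, a last-session cohesion score would come after the month-6 FRS. Hypothesis H3A is worded as prediction, and a score taken after its outcome cannot show that.

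**Working it through.** **Accrual per group.** 400 patients over 24 months (104 weeks) is 400/104 = 3.85 per week. At exactly 4 per week, 400 are reached in 100 weeks. So 4 per week is the trial total, not a rate per site. Dividing by 2 sites and 2 arms gives r = 0.96 to 1.00 GPC patients per site per week.

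**Does 2-4 weeks reproduce?** Take one half-day per site, which fills groups fastest. A patient who joins with j members still to come (j = 0 to 9) waits j/r weeks on average.

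- First member: 9/r = 9.0 to 9.4 weeks.
- Mean over the group: 4.5/r = 4.5 to 4.7 weeks.
- With Poisson arrivals the wait is Gamma(j, rate r). The share waiting 4 weeks or less, averaged over j, is 48-50%.
- All ten start within 4 weeks only if nine arrivals fit into 4 weeks: P{Gamma(9, r) ≤ 4} = 1.7-2.1%.

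The figure does not reproduce under steady accrual.

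**Where month 6 falls.** A calendar month is 4.35 weeks, so month 6 is week 26.1. Session 6 comes five intervals after session 1: 21.7 weeks with calendar months, or 20 weeks with 4-week spacing. If the first session did fall at 2-4 weeks, calendar-month sessions would put session 6 at week 23.7 to 25.7, just before month 6. The latest start that keeps session 6 before month 6 is week 26.1 − 21.7 = 4.35 (unrounded difference), or 26.1 − 20 = 6.1.

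**Share of GPC patients reaching month 6 before session 6.** This is the average over j of P{Gamma(j, r) > slack + visit delay − start lag}, where slack is 4.35 or 6.09 weeks.

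| Accrual, spacing | On due date, no lag | On due date, 2-week lag | Visit 2 weeks late, no lag | Visit 2 weeks late, 2-week lag |
|---|---|---|---|---|
| 3.85/week, calendar | 48.4% | 67.4% | 30.7% | 48.4% |
| 3.85/week, 4-week | 32.9% | 50.8% | 18.4% | 32.9% |
| 4/week, calendar | 46.7% | 66.5% | 28.7% | 46.7% |
| 4/week, 4-week | 30.9% | 49.3% | 16.6% | 30.9% |

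Some lag is built in, since D.4 allows up to 3 business days for the randomization call.

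**More half-days.** Simulation with 100 GPC patients per site (calendar months, no lag, due-date visits) gave these late shares with two/three half-days: 48% if every patient is flexible, 59%/63% if half are, and about 68%/75% if none are.

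**Exposure by month 6.** The same simulation with one half-day and due-date visits, across the spacing and lag combinations at 3.85 per week, gave a mean of 5.0 to 5.6 of 6 sessions held. At least five had been held for 72-92% of patients.

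**Month 12 (week 52.2).** If 2-4 weeks held, session 6 would precede month 12 by 26.4 to 28.4 weeks. Simulated with one half-day, calendar months and no lag, the mean is 25.8 weeks and the 5th-95th percentile range is 19.2 to 30.4.

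**Aim 3 group mean.** The last-session mean follows at least one member's month-6 visit if the first member's wait exceeds the slack. P{Gamma(9, r) > 4.35} is about 97%, and 84-86% for 6.09. Simulation gave 98% and 87%. Both assume no lag and due-date visits.

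**The case against.** **The 2-4 weeks is a forecast, and accrual need not be steady.** This stands. D.5.c presents the figure as experience, and 4 per week is a 24-month average. D.3.c.ii describes recruitment by letter without saying whether mailing is batched. Suppose each site enrolled in waves of 20 (10 GPC) over 3 weeks. Then all would start within 4 weeks and none would be late with a lag of 0-1 week; with a 2-week lag, 0-12% would be late. Over 4 weeks with a 2-week lag it would be 0-31%. A reader might infer that 2-4 weeks is impossible; the documents do not support that. They show only that it does not fit steady accrual, and they state no recruitment pattern that would deliver it.

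**Visits may run late.** This also stands. No window is given, and D.10.b foresees rescheduling. A 2-week delay lowers the shares, as the table shows, but does not remove them.

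**The consequence for the primary outcome may be small.** Largely true. D.5.e covers all five problem-solving cornerstones in sessions 1 and 2, session 6 is forward planning and debriefing, and D.4 mails GPC patients a problem-solving primer after randomization. Enrollment-based visits also give both arms the same clock.

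**Aim 3 is exploratory and its list of predictors is open.** True, but that does not correct the time order of the predictors it does list.

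**Conclusion.** The concern holds as a mismatch between a planning figure and the plan's own accrual rate and group-formation rule. Under steady arrivals and one half-day per site, about half of GPC patients start within 4 weeks, and about 2% of groups have every member do so. About 31-48% of GPC patients would reach month 6 before session 6 with no lag and visits on the due date (49-67% with a 2-week lag), or about 17-31% (31-48%) with visits 2 weeks late. More half-days raise these shares unless patients are flexible; batched recruitment could lower them substantially. Steady arrivals, session spacing, lag, visit timing and flexibility are all assumptions.

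A reader might go further and infer that the primary comparison is biased or underpowered. The documents do not support that. The intent-to-treat comparison remains valid and the sample size is unaffected. Incomplete delivery would, if anything, pull the estimate toward no difference, by an amount that cannot be calculated because no dose-response is given.

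The clearest consequence is confined to exploratory Aim 3. Priority is minor to moderate.

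**What to change.** Reconcile D.1, D.4, D.4.a, D.5.c, D.9.f and section F.

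1. Restate the 2-4 week figure to match planned accrual, or state the recruitment pattern that would deliver it.
2. State that month 6 from enrollment may precede the end of the intervention for a substantial part of the GPC arm. Report, for GPC patients, the number of sessions held before the month-6 visit and the interval from last session to month 12.
3. For Aim 3, use only cohesion scores taken before the outcome visit: for individuals, the last score before that patient's own month-6 visit; for the group mean, the last score before the first member's visit.

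Items 1 and 2 cost wording and a little reporting, with no added patients or visits. Item 3 needs no new data only if the cohesion scale is given at intermediate sessions. D.9.f says the Aim 3 predictors are collected over the course of the intervention, but neither it nor D.8.b.iii.a gives a schedule, so this must be confirmed. If the scale is given only at the first and last sessions, results in which the last-session score follows the outcome should be reported as association, not prediction.

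The downside is that some scores come from an earlier session. If the scale is given at every session (one half-day, calendar months, no lag, due-date visits), simulation has 48% of patients using session 5 or earlier and 15% session 4 or earlier. For the group mean, the last usable session is session 4 or later in 89% of groups.
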